1 SYNOPSIS

TITLE	Retrospective post-market Clinical Investigation for the evaluation of the safety and clinical benefit of Guided Growth Plate System Plus (Orthofix Srl) medical device for the treatment of lower limb bone deformities of the in growing children.
INVESTIGATIONAL DEVICE DESCRIPTION	The GGPSP consists of different sizes of eight-Plate and quad-Plate designed to accept cannulated or solid screws available in a variety of sizes. Plates and screws are available in sterile or non-sterile configuration. The device is designed for the gradual correction of pediatric congenital as well as acquired bone deformities in long bones, provided that the physis (growth plates) are not fused. The plates feature a contoured waist and low profile for pediatric usage. There is a center hole in the plates for a temporary guide pin to be implanted to aid application and removal of the plate. The plates are fixed to the bone over the growth plate by screws. These screws are not locked to the plate, but rather are allowed to swivel and diverge in their position as bone growth occurs. The implant acts like a flexible hinge, halting on one side (hemiepiphysiodesis) or on both sides (epiphysiodesis) the growth plate and thus guiding bone growth. Application and removal of the GGPSP can be performed with Orthofix general orthopaedic instrumentation.
OBJECTIVES AND ENDPOINTS	
Primary objective: evaluate the safety profile of GGPSP.
 
Primary endpoint: percentage of subjects that encountered at least one complication, to be intended as:
 
 · an expected or unexpected serious adverse effect related to the device; · an hardware failure (i.e. breaking, loosening or bending of the plate or of the screws) during follow-up period (from time of plate application to the first post-removal visit). 
Secondary objective: evaluate the clinical benefit of treatment with the GGPSP.
 
Secondary endpoint: percentage of subjects that achieved the treatment goal as defined below:
 
 · for hemiepiphysiodesis, femur and/or tibia angular deformity partially or completely corrected to standard alignment (mMPTA and mLDA between 85° and 89°); · for epiphysiodesis, femur and/or tibia length discrepancy partially or completely corrected to the matching length of the contralateral morphologically normal limb during follow-up period (from time of plate application to the first post-removal visit).
TYPE OF INVESTIGATION	Observational, retrospective, single centre, not controlled.
RAZIONALE	Orthofix is undertaking this retrospective post-market observational Clinical Investigation to evaluate the safety and clinical performance of the GGPSP,

	which is the second version of the GGS and incorporates minor modifications to the original design. The study is aimed to collect Real World Evidence on the usage of the products in a real life surgical setting. Therefore, a retrospective post-market study was chosen as the most appropriate study design to collect the needed data.								
PLANNED INVESTIGATION PERIOD	
Preparation: 4 – 5 months for ethics committee submission preparation
 
Live phase: 10 months to collect the clinical data and write the statistical and clinical report.
								
STUDY DURATION PER SUBJECT	Not Applicable: since this is a retrospective study, all clinical data are already in the patient files at the hospital and patients will not be involved actively in the data collection nor are they subject to further follow-up visits.								
Site	
  
 Hospital	Country	City	Principal Investigator	
   
 Istituto Ortopedico Rizzoli	Italia	Bologna	[name]	
  
	Hospital	Country	City	Principal Investigator	Istituto Ortopedico Rizzoli	Italia	Bologna	[name]
Hospital	Country	City	Principal Investigator						
Istituto Ortopedico Rizzoli	Italia	Bologna	[name]						
INCLUSION CRITERIA	
A patient will be included in the study who:
 
 Was treated with GGPSP to correct deformities of the femur and/or tibia Has concluded treatment with the GGPSP Has a data set available that would allow evaluation of the safety and clinical performance of the device 								
EXCLUSION CRITERIA	
A patient will not be included in the study who:
 
 Was treated with GGPSP to correct only deformities of the upper limbs and not of the lower limbs; Is still undergoing treatment with the GGPSP Does not have a data set available that would allow evaluation of the safety and clinical performance of the device 								
COMPARATIVE DEVICE	I dati di letteratura disponibili per il GGP e per dispositivi equivalenti verranno utilizzati come riferimento ("Stato dell'arte") per l'interpretazione dei dati ottenuti tramite la presente Indagine Clinica.								
CLINICAL PARAMETERS	
 - Age at surgery - Demographical data and BMI - Anamnesis - Indication - Bone (femur / tibia / both) 								

	
 - Location (proximal / distal / both) - Side (L / R / bilateral) - Surgery details (n of implanted plates, duration, complications) - Concomitant treatments - Deformity parameters, where applicable (both at plate application and removal): Hip-knee-ankle (HKA) angle or Anatomic lateral distal femoral angle (aLDFA) or Mechanical axis deviation (MAD) or Mechanical lateral distal femoral angle (mLDFA) or Mechanical medial proximal tibial angle (mMPTA) or Lateral distal tibial angle (LDTA) or Femur-tibia rate or Tibia-fibula rate or Femur, tibia and fibula lenght - Achievement of treatment goal - Treatment time (calculated from implantation to removal) - Complications (both device related and not, leading to premature removal or an unplanned surgery or not)
SAMPLE SIZE CALCULATION	
For the aim of the sample size calculation, the safety profile of GGPSP will be compared to safety data reported in the scientific literature for the treatment of lower limb deformities by the means of guided growth performed by tension band plate. The sample size, therefore, was calculated estimating the required number of subjects so that the primary endpoint of the Study for GGPSP (i.e. percentage of subjects that experienced at least one complication as above described) ranges within the state-of-art safety profile of this treatment, that is, it is within the safety data reported in the literature for its previous version (the GGS) and for equivalent medical devices. Specifically, the scientific literature reports that the percentage of patients treated by a tension band plate for a lower limb deformity that faced at least one complication is between 3% and 12% depending on the many factors, mainly the diversity of the primary diagnosis. Assuming the expected percentage of patients with at least one complication for GGPSP will be 3%, 70 implants was calculated to be the sample size of this study so that the upper limit of the 95% confidence interval for the primary endpoint, based on the exact binomial method, is under 12%. Since each patient may have been treated for the correction of multiple localized deformities in different long bones, it is understood that each eligible subject may contribute to the data collection of multiple implants (average 2). For this reason, approximately 40 patients are expected to be enrolled.

2 Medical Device Information

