8.4 Endpoints

In this Clinical Investigation, the two variables selected as the primary and secondary endpoints, intended to measure the primary and secondary objectives of the Investigation respectively, also correspond to the treatment response measures routinely used in the standard clinical practice of the participating Centre, namely:

- **Primary endpoint (safety measure):**

The safety of the 8-Plate Plus will be assessed by the percentage of subjects who, during the observation period — i.e., from plate implantation to the first follow-up visit after plate removal — experienced at least one complication certainly or potentially related to the investigational device. Such complications are defined as:

- a Serious Adverse Device Effect (SADE), expected or unexpected;
- a hardware failure (e.g., breakage, detachment, or bending of the plate or screws).

- **Secondary endpoint (benefit measure):**

The clinical benefit of treatment with the 8-Plate Plus will be assessed by the percentage of subjects who, during the observation period — i.e., from plate implantation to the first follow-up visit after plate removal — achieved the treatment objective, defined as:

- for hemiepiphysiodesis: partial or complete correction of the angular deformity of the femur and/or tibia towards the standard alignment direction (mMPTA and mL DFA between 85° and 89°);
- for epiphysiodesis: partial or complete correction of femoral and/or tibial length discrepancy in relation to the morphologically normal contralateral limb length.

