8.5 Methods of Endpoint Assessment

The **primary endpoint (safety measure)** of this Clinical Investigation will be assessed as follows:

- The correlation of a serious adverse event with the 8-Plate Plus will be freely determined by the Investigator according to the following options: not related / possibly related / definitely related. Serious events assessed as possibly or definitely related to the 8-Plate Plus will be included in the safety measure calculation.
- It is understood that, for serious events judged as possibly or definitely related to the 8-Plate Plus, the Sponsor reserves the right to supplement the Investigator's assessment with the opinion of an independent orthopaedic surgeon. If the independent orthopaedic surgeon subsequently identifies a surgical technique error in the primary implantation, in agreement with the Investigator, the event initially classified as possibly or definitely related to the 8-Plate Plus may be reclassified as not related and, consequently, excluded from the safety measure calculation. Similarly, serious adverse events due to use not compliant with the manufacturer's Instructions for Use (off-label use) will be excluded from the safety measure calculation.

The **secondary endpoints (benefit measures)** of this Clinical Investigation, as described above, will be assessed by comparing, for each patient, the preoperative radiographs (untreated deformity) with the radiographs collected at the plate removal visit (Visit 4).

The data related to the primary and secondary endpoints, already available in the patients' medical records, will be:

- entered into the validated electronic database provided free of charge by the Sponsor to each Investigator for data collection within the Clinical Investigation;
- analysed using descriptive and/or quantitative statistics and presented with the corresponding confidence intervals (for further details, see the *Statistics* section of this Clinical Investigation Plan).

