8.7 Number of Patients Expected to be Enrolled

The sample size was therefore calculated by estimating the number of implants required so that the confidence limits of the study's primary endpoint for the 8-Plate Plus (i.e., the percentage of subjects who experienced at least one complication certainly or possibly related to the investigational device, as described above) fall within the safety profile of the state of the art for this treatment, namely within the safety data reported in the literature for its predecessor (the GGS) and for other equivalent medical devices.

Specifically, the scientific literature reports that the percentage of patients treated with a tension band plate for a lower limb deformity who experienced at least one device-related complication ranges from 3% to 12%, depending on several factors, primarily the heterogeneity of the primary diagnosis [7].

Assuming that the expected percentage of patients with at least one complication certainly or possibly related to the device for the 8-Plate Plus will be 3%, the sample size calculation showed that, in order for the upper limit of the 95% confidence interval for the primary endpoint (calculated using the exact binomial method) to remain below 12% (i.e., 9.94%), 70 implants are required.

As each patient may have been treated for the correction of multiple deformities located in different long bones, it is understood that each eligible subject may contribute data for more than one implant (on average 2). For this reason, approximately 40 patients are expected to be enrolled.

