The safety profile of the 8-Plate Plus, as measured in the present Clinical Investigation, will be compared with the safety data reported in the scientific literature for the treatment of lower limb deformities by guided growth performed with equivalent tension-band plates.

The sample size calculation was performed in order to estimate the confidence intervals for the primary endpoint (safety outcome related to treatment response) of the 8-Plate Plus and to enable a reliable comparison with the data reported in the literature.

Accordingly, the sample size was determined by estimating the number of implants required so that the confidence intervals for the study primary endpoint with the 8-Plate Plus would fall within the established safety profile for this treatment, namely within the range of safety data reported in the literature for its predecessor (the GGS) and for equivalent medical devices.

Specifically, the scientific literature indicates that the proportion of patients treated with a tension-band plate for lower limb deformity who experience at least one device-related complication ranges between 3% and 12%, depending mainly on the heterogeneity of the underlying diagnosis.

Assuming that the expected proportion of patients experiencing at least one complication with the 8-Plate Plus is 3%, the sample size calculation showed that, in order for the upper limit of the 95% confidence interval for the primary endpoint (calculated using the exact binomial method) to remain below 12% (i.e., 9.94%), a total of 70 implants (in approximately 40 patients) are required.

The clinical data collected during the present Clinical Investigation will be analysed using descriptive statistics:

- the primary endpoint will be presented as a percentage value with its corresponding 95% confidence interval;
- the secondary endpoint will be presented as a percentage value with its corresponding 95% confidence interval.

The clinical data obtained from this Clinical Investigation will be used to complete the evaluation of the clinical performance and safety of the 8-Plate Plus, with the objective of confirming that the device can be considered safe and effective as hypothesised during its development, based on the preclinical evaluations conducted for CE marking.

17 Publication of Results

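### As worded, the primary safety endpoint is narrower than the 3%–12% literature range it is compared with, and the plan does not say which events that range counts

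*Combined protocol and SAP*

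**What the plan says.** **Benchmark.** The sample size entry of the synopsis describes the literature range as the share of those "treated by a tension band plate for a lower limb deformity that faced at least one complication is between 3% and 12" percent, with no condition on relatedness or seriousness. Section 8.7 gives the same range for patients "who experienced at least one device-related complication ranges from 3% to 12" percent and cites reference 7. Section 16 (Statistics) has patients "who experience at least one device-related complication ranges between 3% and 12" percent. None of the three says which event types the range covers.

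**Endpoint.** The synopsis counts a subject who had "an expected or unexpected serious adverse effect related to the device" or a hardware failure. Section 8.4 has the same two components: "a Serious Adverse Device Effect (SADE), expected or unexpected", and "a hardware failure (e.g., breakage, detachment, or bending of the plate or screws"). Under section 8.5, serious events judged possibly or definitely related count.

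**Removals.** Section 8.5 then allows two kinds of serious event to leave the count. If an independent surgeon finds a technique error and the Investigator agrees, the event "may be reclassified as not related and, consequently, excluded from the safety measure calculation". Serious events due to use outside the Instructions for Use ("off-label use) will be excluded from the safety measure calculation") are also removed.

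**Use of the range.** The 12% end sets the sample size: 70 implants, so that the exact 95% upper limit is 9.94%. Section 16 plans to compare the study's safety profile with the literature, with the aim of confirming that the device is safe.

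**The concern.** The study has no control group, so its safety message depends on setting one percentage and its interval beside a published range. That works only if both count the same kind of event. A device-related complication that is neither serious nor a hardware failure fits the benchmark wording in sections 8.7 and 16 but not the endpoint. An event unrelated to the device could also fit the unqualified synopsis wording. Serious events removed under section 8.5 lower the study count further, and nothing in the plan says the literature figures were filtered in the same way. Each difference pulls the study rate down relative to the benchmark as worded. A device at the unfavourable end of the published range could then appear comfortably inside it because of what is counted.

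**Working it through.** **1. Reproduce the plan's figure.** Inputs from sections 8.7 and 16: expected rate 3%, 70 implants, exact binomial 95% interval. Expected count: 0.03 × 70 = 2.1, rounded to 2. The two-sided exact (Clopper-Pearson) upper limit is the 0.975 quantile of Beta(x + 1, n − x). For x = 2 and n = 70 it is the quantile of Beta(3, 68), which is 9.94%. This matches the plan, so the arithmetic is sound and the question is one of definition.

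**2. What an upper limit below 12% means in events.**

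| Units | Events | Exact upper limit |
|---|---|---|
| 70 | 2 | 9.94% |
| 70 | 3 | 12.02% |
| 40 | 0 | 8.81% |
| 40 | 1 | 13.16% |

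So at most 2 events are allowed among 70 units. If the roughly 40 expected patients are the unit, none is allowed.

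**3. Set the definitions side by side.**

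| Event | Benchmark, synopsis wording | Benchmark, 8.7 and 16 wording | Primary endpoint |
|---|---|---|---|
| Serious, device-related | fits | fits | counts, unless removed under 8.5 |
| Hardware failure | fits | fits | counts, serious or not |
| Device-related, not serious, no hardware failure | fits | fits | does not count |
| Unrelated complication | fits if read literally | does not fit | does not count |

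The third row is enough to make the endpoint narrower than both wordings.

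**4. How much overlap the planned figure needs.** The planned limit of 9.94% stays below a like-for-like ceiling only if that ceiling exceeds 9.94%. That requires at least 9.94 / 12 = 83% of the upper literature rate to be events the endpoint would count.

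**5. Illustration under assumptions.** Suppose the true rate on the benchmark definition is 12%, and a share s of those patients meets the endpoint. The endpoint rate is then p = 12% × s. The documents give no value for s, so a range is shown. With 70 independent units the chance of an upper limit below 12% is P(X ≤ 2) for X ~ Binomial(70, p). With 40 patients it is (1 − p)^40.

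| s (assumed) | p | 70 units, at most 2 events | 40 patients, 0 events |
|---|---|---|---|
| 1 (like for like) | 12% | 0.7% | 0.88^40 = 0.6% |
| 3/4 | 9% | 4.3% | 0.91^40 = 2.3% |
| 1/2 | 6% | 20.1% | 0.94^40 = 8.4% |
| 1/3 | 4% | 46.6% | 0.96^40 = 19.5% |

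For example, at 6% and 70 units the probabilities of 0, 1 and 2 events are 0.0132 + 0.0588 + 0.1294 = 0.201.

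**The case against.** The strongest reply is that the plan uses complication as shorthand for one concept throughout. The synopsis defines the word, for the primary endpoint, as a serious device effect or hardware failure, and refers back to that description just before quoting the range. Section 8.7 does much the same. On that reading the range may already be on the endpoint's definition. This stands as a possibility: the synopsis never says that the range covers every complication, and the cited source cannot be checked here. It does not settle the matter, because no section says that the source used the endpoint's definition, and the wording in sections 8.7 and 16 carries no limit to serious events or hardware failures.

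The endpoint is also less narrow than it first looks. Hardware failures count whether or not they are serious, possibly related serious events count, and seriousness includes re-hospitalisation and prolonged hospitalisation. Technique-error removal is conditional on an independent opinion and the Investigator's agreement. Off-label removal may matter little, because the inclusion criteria already require use according to the Instructions for Use. These points reduce the gap without closing it.

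Finally, section 16 is descriptive. It sets no hypothesis test and no pass/fail rule, so 12% is a planning and comparison limit. That is correct, and the probabilities above describe how a reader would be likely to interpret the interval, not a formal error rate. The definition still matters, because the literature comparison and the confirmatory aim are both stated.

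**Conclusion.** The point holds as one of wording and undemonstrated comparability. The same range is described in two ways, neither limited to serious events, and the endpoint is narrower than both as written. An upper limit below 12% on the primary endpoint would therefore not by itself show that the device lies within the published range.

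A reader might go further and infer that the published range is known to count every complication, or that the comparison is certainly biased by a given amount. The documents support neither: the source's event definition is not given, so the size of the mismatch is unknown and could be nil. The 4%, 20% and 47% figures (2%, 8% and 20% with 40 patients) rest on assumed shares, a true benchmark-definition rate of 12% and independent units. They show that the issue could change the safety conclusion; they do not estimate its effect. The calculation behind 9.94% and 70 implants is not in dispute.

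**What to change.** 1. Check the cited source and state, in identical words in the synopsis, section 8.7 and section 16, which events the 3%–12% counts.
2. Keep the rate of serious device effects and hardware failures as the primary endpoint.
3. Add to section 16 the percentage of patients with any device-related complication regardless of seriousness, and the percentage with any complication, each with an exact 95% confidence interval. Show both before any technique-error or off-label removal. Section 8.10 already collects device-related and unrelated complications, so no new data are needed.
4. Base the comparison with 3%–12% on whichever rate matches the source's definition. If the source does match the serious-effect and hardware-failure definition, say so and keep the current comparison.

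The cost is one or two table rows and reconciled wording in three places. The rate compared with the literature may turn out less favourable.

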2.1 Medical Device Identification

The medical device under investigation in this Clinical Investigation is the “Guided Growth Plate System Plus” (GGPSP), also known as the “eight-Plate Guided Growth System +™”, hereinafter referred to as 8-Plate Plus. 8-Plate Plus represents the new generation of the guided growth system known as the “Guided Growth System” (GGS), also referred to as 8-Plate. Although the two devices have been CE marked separately, they have been deemed equivalent based on a comparative analysis (Ref. CER-13_Rev. 04) and, as such, have been grouped into a single product family—namely, the Guided Growth Plate Systems (hereinafter GGPS, REF DMF-13), which includes both the GGS and GGPSP systems. The 8-Plate Plus is a plate-and-screw system classified as a Class IIb medical device, manufactured and marketed by Orthofix S.r.l. in European Union markets and selected non-EU markets since May 2017.

